7.2.3. Objective Response Rate

A participant is considered an objective responder if they have a best overall response of CR or PR confirmed by at least 1 repeat assessment \geq 28 days later according to RECIST v1.1 as determined by the investigator. The ORR will be calculated separately for each cohort and dose level.

7.3. Analysis of the Secondary Efficacy Parameters

[figure not shown]
7.3.1. **Duration of Response**

Duration of response is defined as the time from the earliest date of CR or PR confirmed by at least 1 repeat assessment \geq 28 days later until the earliest date of disease progression by investigator assessment per RECIST v1.1, or death due to any cause, if occurring sooner than progression. Partial death dates will be handled using the rules described in Section 4.1.4.

For participants who have not had disease progression and are still alive at the time of the analysis, DOR will be censored on the day of last evaluable disease assessment. For participants who have discontinued the study or have started other anticancer treatment, DOR will be censored on the day of last evaluable disease assessment documenting absence of PD before the discontinuation or the start of the new anticancer treatment. The KM estimate of median DOR and its 95% CI will be calculated using the KM method if the number of responders is ≥ 5 . Duration of response will be listed for each responder.

7.3.2. Disease Control Rate

Disease control rate is defined as the percentage of participants with a best overall response of CR or PR confirmed by at least 1 repeat assessment \geq 28 days later, or SD for \geq 12 weeks, by investigator assessment per RECIST v1.1. The DCR will be summarized separately for each cohort and dose level.

9. SAFETY AND TOLERABILITY

Appendix A provides a list of data displays. Sample data displays are included in a separate document.

9.1. General Considerations

The clinical safety data (ie, routine laboratory tests and AEs) will be summarized using descriptive statistics (eg, mean, frequency) using the safety evaluable population.

9.2. Adverse Events

9.2.1. Adverse Event Definitions

A TEAE is any AE either reported for the first time or worsening of a pre-existing event after the first dose of study drug up to 90 days after the last dose of study drug or until the start of new anticancer therapy, whichever occurs first. Analysis of AEs (as discussed below) will be limited to TEAEs, but data listings will include all AEs regardless of their timing in relation to study drug administration. For purposes of analysis, all AEs will be considered TEAEs unless the AE can unequivocally be defined as not treatment-emergent.

Adverse events will be tabulated by MedDRA SOC and PT. Severity of AEs will be graded using the National Cancer Institute CTCAE v5 using Grades 1 through 5. The CTCAE reporting guidelines and grading details are available on the Cancer Therapy Evaluation Program website.

The subset of AEs considered by the investigator to be related to study drug will be considered to be treatment-related AEs. If the investigator does not specify the relationship of the AE to study drug, the AE will be considered to be treatment-related.

Any missing onset date, causality, or severity must be queried for resolution. Unresolved missing causality and severity will be handled according to the following rules:

- An unresolved missing causality will be considered treatment-related.
- An unresolved missing severity will be identified as an unknown severity.

9.2.2. Immune-Related Adverse Events

Number (%) of participants reporting any irAEs will be tabulated by immune-related category and PT. Potential irAEs will be identified according to a sponsor-defined list of terms. Final clinical irAE review details will be outlined in the CSR.

9.2.3. Adverse Event Summaries

Overall summaries of AEs and irAEs by cohort, dose, and total will include the following:

- Participants who had a TEAE/irAE
- Participants who had a serious TEAE/irAE
- Participants who had a Grade 3 or higher TEAE/irAE
- Participants who had a treatment-related TEAE

- Participants who had a serious treatment-related TEAE
- Participants who had a Grade 3 or higher treatment-related TEAE
- Participants who had a fatal TEAE/irAE
- Participants who had a TEAE/irAE leading to dose reduction
- Participants who had a TEAE/irAE leading to dose interruption
- Participants who had a TEAE/irAE leading to discontinuation of INCB086550
- Participants who had a TEAE/irAE leading to dose reduction, interruption, or discontinuation of INCB086550

The following summaries will be produced by MedDRA SOC and/or PT or irAE category:

- Summary of TEAEs by SOC and PT
- Summary of TEAEs by PT in decreasing order of frequency
- Summary of serious TEAEs by SOC and PT
- Summary of serious treatment-related TEAEs by PT in decreasing order of frequency
- Summary of TEAEs with a fatal outcome by SOC and PT
- Summary of TEAEs leading to dose modification of INCB086550 by SOC and PT
- Summary of TEAEs leading to discontinuation of INCB086550 by SOC and PT
- Summary of sponsor-defined irAEs by category and PT

9.3. Clinical Laboratory Tests

9.3.1. Laboratory Value Definitions

Laboratory values and change from baseline values will be summarized descriptively by visit. Baseline will be determined according to Section 4.1.3. If there are multiple values that meet the criteria for baseline, additional rules may be provided after consultation with the medical monitor to delineate which value will be defined as baseline. Laboratory test values will be assessed for severity using Grades 1 through 4 using CTCAE v5 when applicable.

9.3.2. Laboratory Value Summaries

A certified laboratory local to the investigative site will perform all clinical laboratory assessments for safety (ie, blood chemistries, hematology assessments, coagulation tests, endocrine function, and urinalysis).

Any laboratory test results and associated normal ranges from local laboratories will be converted to SI units.

Shift tables will be presented showing change in CTCAE grade from baseline to worst grade postbaseline for hematology and chemistry laboratory assessments. Separate summaries for abnormally high and abnormally low laboratory values will be provided when the laboratory

parameter has both high and low grading criteria. The denominator for the percentage calculation will be the number of participants in the baseline category.

9.3.3. Potential Drug-Induced Liver Injuries

Participants with elevated alanine aminotransferase or aspartate aminotransferase $\geq 3 \times ULN$ and alkaline phosphatase $< 2 \times ULN$ accompanied by total bilirubin $\geq 2 \times ULN$ within ± 7 days will be listed by cohort and dose.

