APPENDIX D. MANAGEMENT OF POTENTIAL HY'S LAW CASES

INTRODUCTION

During the course of the study, the investigator will remain vigilant for increases in liver biochemistry. The investigator is responsible for determining whether a participant meets PHL criteria at any point during the study.

The investigator participates, in conjunction with Incyte clinical project and pharmacovigilance representatives, in the review and assessment of cases fulfilling PHL criteria to ascertain whether there is an alternative explanation for the elevations in liver biochemistry other than drug-induced liver injury caused by the study drug.

The investigator fulfils requirements for the recording of data pertaining to PHL or Hy's law cases and AE/SAE reporting according to the outcome of the review and assessment in line with standard safety reporting processes.

DEFINITIONS

For the purpose of this process definitions are as follows

Potential Hy's Law

An increase in AST or ALT $> 3 \times \text{ULN}$ and total bilirubin $> 2 \times \text{ULN}$ at any point during the study. The elevations do not have to be at the same time or within a specified timeframe.

Hy's Law

An increase in AST or ALT $\geq 3 \times \text{ULN}$ and total bilirubin $> 2 \times \text{ULN}$, where no other reason can be found to explain the combination of increases (eg, elevated serum ALP indicating cholestasis, viral hepatitis, another drug).

ACTIONS REQUIRED IN CASES OF AST OR ALT $> 3 \times \text{ULN}$ OR TOTAL BILIRUBIN $\geq 2 \times \text{ULN}$

Identification and Determination of Potential Hy's Law

To identify cases of AST or ALT $> 3 \times \text{ULN}$ or total bilirubin $> 2 \times \text{ULN}$ and consequently determine whether the participant meets PHL criteria, please follow the instructions below:

- Review the laboratory report and if a participant has AST or ALT $> 3 \times \text{ULN}$ OR total bilirubin $> 2 \times \text{ULN}$ at any visit:
 - Determine without delay whether the participant meets PHL criteria by reviewing laboratory reports from all previous visits.
 - Enter the laboratory data into the laboratory eCRF as soon as possible.

Potential Hy's Law Criteria Not Met

If the participant has NOT had AST or ALT $\geq 3 \times \text{ULN}$ AND total bilirubin $> 2 \times \text{ULN}$ at any point in the study (the elevations do not have to be at the same time or within a specified timeframe), irrespective of ALP, please follow the instruction below:

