- Perform follow-up on subsequent laboratory results according to the guidance provided in Section 8.3.6.

Potential Hy's Law Criteria Met

If the participant has had AST or ALT $\geq 3 \times$ ULN AND total bilirubin $> 2 \times$ ULN at any point in the study (the elevations do not have to be at the same time or within a specified timeframe), irrespective of ALP, please follow the instruction below:

- Have participant interrupt study drug.
- Notify Incyte study team without delay.
 - The investigator, or designee, should contact the medical monitor to discuss and agree upon an approach for the study participant's follow-up and the continuous review of data.
- Monitor the participant until liver biochemistry parameters and appropriate clinical symptoms and signs return to normal or baseline levels, or as medically indicated.
- Investigate the etiology of the event and perform any relevant diagnostic investigations as discussed with the medical monitor.
- Enter the laboratory data into the laboratory CRF as soon as possible.
- If at any time (in consultation with the medical monitor) the PHL case meets serious criteria, report it as an SAE using standard reporting procedures.

REVIEW AND ASSESSMENT

No later than 3 weeks after the biochemistry abnormality is initially detected and the criteria for PHL is met, the medical monitor, Incyte pharmacovigilance physician, and investigator will discuss and review available data and agree on whether there is an alternative explanation for the elevations in liver biochemistry other than drug-induced liver injury caused by the study drug. Participant matter experts will be included in the review as appropriate.

Evaluation of Alternative Causes

In order to gather additional clinical information to seek other possible causes of the observed liver test abnormalities, the following alternative etiologies should be considered, including but not limited to,

- Active viral hepatitis
- Alcoholic and autoimmune hepatitis
- Hepatobiliary disorders
 - Biliary tract disease, such as migration of gallstones or intrahepatic lesions, more often causes cholestatic injury initially and should be investigated with gall bladder and ductal imaging studies, especially if alkaline phosphatase is increased. Malignant interruption of the biliary tract also should be considered.
- Concomitant treatment

- Other causes such as systemic infections (bacterial, fungal, viral), nonalcoholic steatohepatitis, and cardiovascular diseases

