Actions After Review and Assessment

According to outcome of the review and assessment, please follow the instructions below:

If there **is** an agreed alternative explanation for the AST or ALT **and** total bilirubin elevations, a determination of whether the alternative explanation is an AE will be made and subsequently whether the AE meets the criteria for a SAE.

- If the alternative explanation is not an AE, record the alternative explanation on the appropriate CRF if possible.
- If the alternative explanation is an AE/SAE, record the AE/SAE in the eCRF accordingly and follow the standard study processes.
- Have participant resume study drug as per Protocol guidelines.

If it is agreed that there is no explanation that would explain the AST or ALT and total bilirubin elevations:

- Have participant permanently discontinue study drug and perform end-of-treatment procedures.
- Report an SAE (report term "Hy's Law").
 - The 'medically important' serious criterion should be used if no other serious criteria apply.
 - As there is no alternative explanation for the Hy's law case, a causality assessment of related should be assigned.
- If there is an unavoidable delay of over 3 weeks in obtaining the information necessary to assess whether or not the case meets the criteria for a Hy's law case, then it is assumed that there is no alternative explanation until such time as an informed decision can be made. Report an SAE (report term "Potential Hy's Law") applying serious criteria and causality assessment as per above.

ACTIONS REQUIRED FOR REPEAT EPISODES OF AST OR ALT $> 3 \times$ ULN AND/OR TOTAL BILIRUBIN $> 2 \times$ ULN

The requirement to conduct follow-up, review, and assessment of a repeat occurrence(s) of PHL is based on the nature of the alternative cause identified for the previous occurrence.

If the alternative cause for the previous occurrence of PHL was not chronic or progressing malignant disease, please follow the process for PHL review and assessment as described in this appendix.

If the alternative cause for the previous occurrence of PHL was chronic or progressing malignant disease, please follow the instructions below:

- Determine whether there has been a significant change* in the participant's condition.
 - If there is no significant change, no action is required.

- If there is a significant change, follow the process described for PHL review and assessment as described in this appendix.

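### The liver-injury listing in SAP 9.3.3 omits potential Hy's law cases with ALP at or above 2×ULN or elevations more than 7 days apart, and SAP 11.1 does not say so

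*SAP*

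**What the plan says.** **Protocol Appendix D** defines potential Hy's law as raised ALT or AST together with raised total bilirubin at any point in the study, with no time window: "The elevations do not have to be at the same time or within a specified timeframe". The paragraph on what to do when the criteria are met adds that ALP plays no part: "the elevations do not have to be at the same time or within a specified timeframe), irrespective of ALP". The required action is "Have participant interrupt study drug", followed by case review. Under the separate definition of Hy's law proper, "elevated serum ALP indicating cholestasis" is one example of another reason that may explain the combination.

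**Protocol 10.4.4.2** says possible Hy's law events will be listed and leaves the criteria to the SAP.

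**SAP 9.3.3** sets them: ALT or AST at least 3×ULN, "alkaline phosphatase $< 2 \times ULN$ accompanied by total bilirubin" at least 2×ULN, and a window of plus or minus "7 days will be listed by cohort and dose". The output is Listing 2.8.1.4.

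**SAP 11.1** reports that the Hy's law analysis was replaced by a new company standard for potential drug-induced liver injury. It mentions neither the ALP limit nor the window.

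**The concern.** Listing 2.8.1.4 is the only output in SAP Appendix A that selects participants on combined ALT/AST and bilirubin elevation. The chemistry shift table (3.3.3.2) and the chemistry listing (2.8.1.2) do not make that selection. A participant can therefore meet Appendix D, have drug interrupted and go through case review, and still be absent from the listing where a reader would look. An empty Listing 2.8.1.4 could be taken to mean that no potential Hy's law case arose, and SAP 11.1 gives no warning against that.

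The eligibility rules make the ALP condition more than theoretical. Participants may enter with ALP already above the SAP cut, and Table 8 links its higher ALP limit to bone metastases, so a raised ALP here need not mean cholestasis. Appendix D settles that question at case review; the SAP rule settles it from the ALP value alone.

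**Working it through.** There is no planned figure to reproduce. The check compares two case definitions and then looks at how often chemistry is drawn.

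**1. The rules side by side**

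| | Appendix D | SAP 9.3.3 |
|---|---|---|
| ALT/AST | >3×ULN (definition); ≥3×ULN (criteria-met paragraph) | ≥3×ULN |
| Total bilirubin | >2×ULN | ≥2×ULN |
| ALP | any | <2×ULN, draw not stated |
| Timing | any time on study | within 7 days |

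**2. Test cases** (multiples of ULN; illustrations of the rules, not frequencies)

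| Case | Appendix D, >3 | Appendix D, ≥3 | SAP |
|---|---|---|---|
| ALT 6, bilirubin 3, ALP 2.2, same day | yes | yes | **no** |
| ALT 4 with bilirubin 1.5, then ALT 2.5 with bilirubin 2.5, 8 or 14 days later, ALP 1 | yes | yes | **no** |
| Same, 7 days apart | yes | yes | yes |
| ALT 3.0, bilirubin 2.5, ALP 1 | no | yes | yes |
| ALT 3.0, bilirubin 2.0, ALP 1 | no | no | yes |

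Because SAP 9.3.3 does not say at which draw ALP is read, three readings were tried: ALP at the ALT draw, and the lowest and the highest ALP in the window. All gave these results.

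**3. Are there other routes out?** Both rules were applied to a grid of ALT/AST 2.9, 3, 4, 6; bilirubin 1.9, 2, 3; ALP 1, 1.9, 2, 2.4, 4.9; and gaps of 0, 6, 7, 8, 14, 21 days. With the >3 threshold, 2 × 1 × 5 × 6 = 60 combinations meet Appendix D, and 2 × 1 × 2 × 3 = 12 of them also meet the SAP. All 48 others fail on ALP ≥2×ULN, on a gap over 7 days, or on both. With ≥3 the counts are 90, 18 and 72, for the same reasons. Combinations that only the SAP catches lie exactly on a boundary (ALT/AST = 3 or bilirubin = 2). The counts reflect the grid, not expected rates.

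**4. ALP at entry.** Table 8 allows ALP <2.5×ULN for anyone and <5×ULN with bone metastases (with medical monitor approval if there are also hepatic metastases). Entry values from 2.0 to below 2.5×ULN, or to below 5×ULN with bone metastases, are already outside the SAP rule.

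**5. The 7-day window against the visit schedule.** Minimum gap = nominal gap − late allowance at the current visit − early allowance at the next (Tables 3–6).

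- Schedules A and B, Cycles 2–6: 14 − 3 − 3 = 8 days.
- Schedules A and B, Cycle 7 onward: 28 − 3 − 3 = 22 days.
- Schedules C and D, Cycle 2 onward: 21 − 3 − 3 = 15 days.
- Schedule A, Cycle 1 Day 14 to Cycle 2 Day 1: 15 − 3 − 3 = 9 days (continuous and 3-week) or 15 − 0 − 3 = 12 days (2-week).
- Schedule C, Cycle 1 Day 14 to Cycle 2 Day 1: minimum 8 − 0 − 3 = 5, maximum 8 + 3 + 3 = 14 days.
- Day 1 to Day 7 of Cycle 1, where Protocol 8.3.6 lets the Day 1 draw precede dosing by up to 48 hours: Schedule B, 6 − 3 = 3 to 6 + 3 + 2 = 11 days; Schedule D, 6 − 1 = 5 to 6 + 0 + 2 = 8 days.

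These figures assume no cycle delay and that the 72-hour laboratory allowance lies inside the 3-day window. From Cycle 2, two scheduled cycle-visit draws therefore cannot pair within 7 days. Other draws can: the scheduled end-of-treatment chemistry, repeats under Table 10 (hepatitis), Table 12 (creatinine) and Section 8.3.6, and Appendix D monitoring. A case drops out on timing only if no draw with ALT/AST ≥3×ULN lies within 7 days of one with bilirubin ≥2×ULN.

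**6. Where an omitted case would still appear.** Unexplained cases must be reported as SAEs under Appendix D (Listing 2.7.2). For explained ones, "If the alternative explanation is an AE/SAE, record the AE/SAE in the eCRF accordingly". In addition, Protocol 9.1 makes an abnormal laboratory result an AE if it requires a change in study drug, and Appendix D requires interruption once the criteria are met. Most omitted cases should therefore be in Listings 2.7.1 and 2.7.4. The remainder are findings put down to the underlying disease and no more severe than expected, and events related to progression, which Protocol 9.1 excludes from AE reporting. For a non-AE explanation, "If the alternative explanation is not an AE, record the alternative explanation on the appropriate CRF if possible". Such cases may appear only in the chemistry (2.8.1.2) and dosing (2.5.2) listings.

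**The case against.** The protocol hands the listing criteria to the SAP, the SAP supplies them, and SAP 11.1 announces the change. A reader can compare the two texts. Appendix D is a deliberately broad trigger for interruption and case review, whereas a listing may reasonably be more specific, and Appendix D itself names cholestasis as an alternative reason. The study was terminated early with minimal enrollment and is being reported in a synoptic CSR. The missing cases are mostly in the AE listings, and those that are not tell least about drug injury.

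Most of this stands. It rules out several stronger readings that a reader might infer:

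- *The SAP breaks a protocol commitment.* It does not; Protocol 10.4.4.2 delegates the criteria.
- *Liver-injury cases vanish from the report.* Unexplained cases are SAEs, and most others should be AEs with a drug interruption.
- *From Cycle 2 only unscheduled repeats can bring values within 7 days.* The end-of-treatment draw is scheduled and can also do so.
- *The SAP rule is a strict subset of Appendix D.* At exact boundary values it is slightly wider than the Appendix D definition.

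The objection does not remove the gap itself. The one listing built for this purpose leaves out protocol-defined cases, in a population allowed to enter above the ALP cut, and the section on changes does not say so.

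**Conclusion.** The point holds as an optional, low-cost improvement. SAP 9.3.3 omits Appendix D cases in two situations: ALP at or above 2×ULN, and no ALT/AST elevation within 7 days of a bilirubin elevation. The first matters more, because it can exclude a participant for the whole study; the second is narrow.

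No capture rate can be given. The documents report no liver data for this study, and the number of affected participants may be zero. The conclusion on ALP takes ALP as read at or around the event, which SAP 9.3.3 leaves open. The view that the loss is limited rests on sites recording the Appendix D interruption and the related AE as the protocol requires. The cases most exposed are those attributed to the tumour, which is most plausible in participants with HCC or liver metastases. Case management under Appendix D is unaffected.

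**What to change.** 1. Widen Listing 2.8.1.4 to ALT or AST ≥3×ULN and total bilirubin ≥2×ULN at any time on study, with any ALP. Using ≥ for both keeps every case that SAP 9.3.3 now lists.
2. Add two flags: company standard met, and Appendix D met.
3. Where the shell lacks them, add columns for baseline ALT/AST and ALP, ALP at the qualifying draw, and days between the elevations. Baseline ALT/AST is needed because Appendix D speaks of an increase, while Table 8 lets participants with HCC or liver metastases enter with values up to 5×ULN.
4. State in SAP 9.3.3 at which draw ALP is read.
5. Before programming the Appendix D flag, have the sponsor reconcile the >3×ULN and ≥3×ULN thresholds within Appendix D.
6. State in SAP 11.1 how the two rules differ and which cases only Appendix D captures.

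The cost is a few sentences in SAP 9.3.3 and 11.1 and some rows and columns in one listing, from data already collected. SAP Appendix A lets shell changes that do not affect the nature of the analysis go ahead without an amendment, but the wider selection rule is a text change to 9.3.3. The downside is a few added rows with cholestatic or tumour-related explanations, which the flags and columns make visible.
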